## 2 Trial Objectives

### 2.1 Primary Objective

To compare the rate of any fever (temperature  $\geq 100.4^{\circ}\text{F}$  [ $38.0^{\circ}\text{C}$ ]) following the 0.5-mL dose of Fluzone Quadrivalent vaccine to that following the 0.25-mL dose of Fluzone Quadrivalent vaccine during the 7 days after either vaccination (Dose 1 and Dose 2 combined) in subjects 6 to < 36 months of age.

The endpoint for the primary objective is presented in [Section 4.1](#).

## 2.2 Secondary Objective

To compare antibody responses induced by the 0.5-mL dose of Fluzone Quadrivalent vaccine to those induced by the 0.25-mL dose of Fluzone Quadrivalent vaccine as assessed by geometric mean titer (GMT) ratios and seroconversion rate differences after the final vaccination in subjects 6 to < 36 months of age.

The endpoints for the secondary objectives are presented in [Section 4.2](#).

## 2.3 Observational Objectives

### 2.3.1 Safety

To describe the safety of 2 different dose levels of the 2016–2017 formulation of Fluzone Quadrivalent vaccine in subjects 6 to < 36 months of age.

The endpoints for the observational safety objective are presented in [Section 4.3.1.2](#).

### 2.3.2 Immunogenicity

To describe the immunogenicity of 2 different dose levels of the 2016–2017 formulation of Fluzone Quadrivalent vaccine in subjects 6 to < 36 months of age.

The endpoints for the observational immunogenicity objective are presented in [Section 4.3.2.1](#).

### 2.3.3 Serum Collection

There are no endpoints for the serum collection objective.

## 3 Description of the Overall Trial Design and Plan

### 3.1 Trial Design

This will be a Phase IV, randomized, observer-blinded, 2-arm, multi-center trial to evaluate the safety and immunogenicity of 2 different dose levels of Fluzone Quadrivalent vaccine in approximately 2190 healthy children 6 to < 36 months of age.

### 3.2 Trial Plan

Using a pre-programmed interactive response technology (IRT) system, subjects will be randomly assigned in a 1:1 ratio to either 1 of the following groups:

- Group 1: 0.25 mL of Fluzone Quadrivalent vaccine (approximately 1095 subjects)
- Group 2: 0.5 mL of Fluzone Quadrivalent vaccine (approximately 1095 subjects)

Enrollment will be stratified by age at each site so that approximately 50% of subjects at each site will be 6 to < 24 months of age and approximately 50% of subjects at each site will be 24 to < 36 months of age. If necessary to achieve 50% overall enrollment of subjects 6 to < 24 months of age, individual sites may be permitted to deviate from this ratio.

All subjects will receive 1 intramuscular dose of Fluzone Quadrivalent vaccine (0.25 mL [Group 1] or 0.5 mL [Group 2]) during Visit 1. For subjects for whom 2 doses of influenza vaccine are recommended per ACIP guidance, a second dose of Fluzone Quadrivalent vaccine (same 0.25-mL or 0.5-mL dose as administered at Visit 1) will be administered during Visit 2 (28 [window, 28–35] days after Visit 1).

Blood specimens will be obtained from a planned subset of approximately 1600 subjects randomly selected by an IRT system (half in Group 1 and half in Group 2) prior to the first vaccination and 28 (window, 28–35) days following the final vaccination (Visit 2 for subjects receiving 1 dose; Visit 3 for subjects receiving 2 doses) and assayed for immunogenicity.

Solicited AE information will be collected for 7 days after each vaccination. Unsolicited AE information and serious adverse event (SAE) information will be collected from Visit 1 to Visit 2 for subjects receiving 1 dose or from Visit 1 to Visit 3 for subjects receiving 2 doses.

Note: Any SAE that occurs after a subject has completed the study but that is likely to be related to the product is to also be reported to the Sponsor.

**Table 3.1: Study Procedures - Trial Flow Chart for Subjects 6 to < 36 Months of Age: 2 or 3 Visits, 1 or 2 Vaccinations, 2 Groups**

Visit Number	All Subjects		Subjects Receiving 1 Dose of Influenza Vaccine	Subjects Receiving 2 Doses of Influenza Vaccine		
	Visit 1	Telephone Contact	Visit 2	Visit 2	Telephone Contact	Visit 3
Trial Timelines	Day 0	Visit 1 + 8 days	Visit 1 + 28 days	Visit 1 + 28 days	Visit 2 + 8 days	Visit 2 + 28 days
Time Windows	--	+ 8 to 10 days	+ 28 to 35 days	+ 28 to 35 days	+ 8 to 10 days	+ 28 to 35 days
Informed consent	X					
Inclusion & Exclusion Criteria	X					
Demographic data	X					
Medical history	X					
Influenza vaccination history	X					
History-directed physical examination	X			X		
Temperature	X			X		
Allocation of subject number/Randomization	X					
Blood sample (BL) a	BL1		BL2			BL2
Vaccination b,c	X			X		
Immediate surveillance (20 minutes)	X			X		
Diary card (DC) provided	DC1			DC2		
Telephone contact d		X			X	

	All Subjects		Subjects Receiving 1 Dose of Influenza Vaccine	Subjects Receiving 2 Doses of Influenza Vaccine		
			DC1	DC1		DC2
Diary card reviewed and collected			X	X		X
Interim history			X	X		X
Termination record e			X			X
Serious adverse events	To be reported throughout the study period					

a A blood sample, approximately 5 mL, will be collected from subjects randomly assigned to the immunogenicity subset at Visit 1, prior to vaccination, and at either Visit 2 (for subjects receiving 1 influenza vaccine dose) or at Visit 3 (for subjects receiving 2 influenza vaccine doses).

b Group 1 will receive a 0.25-mL dose of Fluzone Quadrivalent vaccine at Day 0; Group 2 will receive a 0.5-mL dose of Fluzone Quadrivalent vaccine at Day 0.

c One or 2 doses of influenza vaccine will be administered according to the Advisory Committee on Immunization Practices guidance in effect during the study. If 2 doses of influenza vaccine are indicated, 1 dose will be administered during Visit 1 and the second dose (of the same volume as the first dose) will be administered approximately 28 days later during Visit 2.

d The subject's parent/guardian will be contacted by telephone on Day 8 after vaccination as a reminder to complete the diary card and to bring it with them to the next visit.

e The termination form will be completed at Visit 2 for subjects receiving 1 dose of influenza vaccine or at Visit 3 for subjects receiving 2 doses of influenza vaccine.

## 4 Endpoints and Assessment Methods

### 4.1 Primary Endpoint and Assessment Methods

#### 4.1.1 Primary Safety Endpoint - Body Temperature

The primary (safety) objective is presented in [Section 2.1](#).

Rates of any fever (temperature  $\geq 100.4^{\circ}\text{F}$  [ $38.0^{\circ}\text{C}$ ]) during the 7 days after either vaccination (Dose 1 and Dose 2 combined) in each vaccine group.

#### 4.1.2 Body Temperature Measurement Methods and Assessment

After each vaccination, the subject's parent/guardian will be provided with a safety diary card and will be instructed how to use them.

Parents/guardians are to measure body temperature once per day, preferably always at the same time. The optimal time for measurement is the evening, when body temperature is the highest. Temperature is also to be measured at the time of any apparent fever. The observed daily temperature and the route of measurement are to be recorded in the diary card, and the highest temperature will be recorded by the site in the electronic case report form (eCRF) for every day (Day 0 to Day 7). The preferred route for temperature measurement in this trial is rectal. In cases where a rectal temperature cannot be obtained, a non-preferred route (e.g., axillary) may be used. Pre-vaccination temperature is also to be systematically collected by the Investigator in the eCRF for all subjects. Tympanic thermometers must not be used.

All body temperatures reported as  $< 90^{\circ}\text{F}$  will be transformed / set as missing except those temperatures identified as having been reported in degrees Celsius ( $^{\circ}\text{C}$ ). Temperatures reported in  $^{\circ}\text{C}$  will be transformed into degrees Fahrenheit ( $^{\circ}\text{F}$ ) using the formula:

$$(\text{Temperature } (^{\circ}\text{C}) \times (9/5)) + 32 = \text{Temperature } (^{\circ}\text{F})$$

The primary endpoint of fever during the solicited period (Day 0 to Day 7) will be derived based on a conservative approach, as follows:

- If at least 1 of the daily measurements is  $\geq 100.4^{\circ}\text{F}$ , then the value of fever=Yes
- If one or more days during the solicited period have non-missing body temperatures that are all  $< 100.4^{\circ}\text{F}$  AND the parent/guardian of the subject answered "No" to the presence of fever, then the value of fever=No
- If all days during the solicited period have missing body temperatures, then the value of fever=Missing, even if the parent/guardian of the subject answered "No" to the presence of fever

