Additionally, the following important medical events are to be considered as SAEs and reported to the Sponsor according to the procedure described in [Section 10](#):

- New onset of GBS, encephalitis/myelitis (including transverse myelitis), neuritis (including Bell's palsy, optic neuritis, and brachial neuritis), thrombocytopenia, vasculitis, convulsions (including febrile convulsions), and anaphylaxis or other hypersensitivity/allergic reactions

Adverse Reaction:

All noxious and unintended responses to a medicinal product related to any dose should be considered ARs.

(The phrase “responses to a medicinal product” means that a causal relationship between a medicinal product and an AE is at least a reasonable possibility.)

Unexpected Adverse Reaction:

An unexpected AR is an AR, the nature or severity of which is not consistent with the applicable product information (e.g., Investigator's Brochure for an unapproved investigational medicinal product).

The following additional definitions are used by Sanofi Pasteur:

Solicited Reaction:

A solicited reaction is an event that is prelisted in the eCRF. The assessment of these AEs post-vaccination is mandatory. A solicited reaction is defined by a combination of:

- Symptom and
- Onset post-vaccination

Examples of solicited reactions include injection site pain between Day 0 and Day 7 post-vaccination, or headache between Day 0 and Day 7.

^a All medical events leading to hospitalizations will be recorded and reported as SAEs, with the exception of: hospitalization planned before inclusion into the study or outpatient treatment with no hospitalization.

^b “Persistent or significant disability or incapacity” means that there is a substantial disruption of a person's ability to carry out normal life functions.

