9.3.1.3.2 Reactogenicity (Solicited Reactions From Day 0 to Day 7 After Each Vaccination)

After each vaccination, the subject's parent/guardian will be provided with a safety diary card, a digital thermometer, and a flexible ruler, and will be instructed how to use them. The following items will be recorded by the parent/guardian in the diary card on the day of vaccination and for the next 7 days (i.e., Day 0 to Day 7) until resolution:

- Daily temperature, with the route by which it was taken
- Daily measurement or intensity grade of all other solicited injection site and systemic reactions

- Action taken for each event, if any (e.g., medication)

The action taken by the subject's parent/guardian to treat any **solicited reactions** will be classified in the eCRF using the following scale:

0: None

1: Medication (self-medication with an existing prescription or over-the-counter medication)

2: Health care provider contact (no new medication prescribed)

3: Health care provider contact and prescription of a new medication (health care provider instructed subject to take a new medication, either an over-the-counter medication or one requiring a written prescription)

4: Hospitalization (inpatient)

Parents/guardians will be contacted by telephone approximately 8 days after each vaccination to remind them to record all safety information in the diary card.

If the timing of the telephone call should fall on a weekend or a holiday, the call should be made on the next business day. If contact is not made on the designated day, study staff will continue calling until contact is made. Every telephone attempt and its outcome will be documented in the source document.

[Table 9.1](#) and [Table 9.2](#) present, respectively, the injection site reactions and systemic reactions that are prelisted in the diary cards and eCRF, together with the intensity scales.

Table 9.1: Solicited Injection Site Reactions: Terminology, Definitions, and Intensity Scales (Subjects 6 to < 36 Months of Age)

eCRF term (MedDRA lowest level term [LLT])	Injection site tenderness	Injection site erythema	Injection site swelling
Diary card term	Tenderness	Redness	Swelling

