### 5.1.3.1 Safety Analysis

The safety analysis will report the occurrence of solicited reactions and the incidence of unsolicited AEs between Visit 1 and Visit 2 (or between Visit 1 and Visit 3 for those subjects receiving 2 doses).

To avoid any under-estimation of the incidences, the number of subjects with documented safety will be used as denominator for the frequencies.

- For solicited reactions, the denominator will be the total number of subjects who have non-missing data for the endpoint considered
- For unsolicited AEs, the denominator will be the total number of subjects who were vaccinated at the dose analyzed.

The safety tables will be produced using a subject approach, i.e., number of subjects who experienced at least 1 safety event during a considered period.

The 2-sided 95% CIs for the percentages will be calculated using the exact binomial method (Clopper-Pearson method).

Additional safety tables, which will be based on analyses that exclude safety data from Site 009, will be presented in the CSR appendices. Specifically, these tables will be those that provide overall safety overviews/summaries and those that describe solicited reactions after any vaccination by maximum intensity.

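### Read literally, the fever derivation drops a child with no daily temperature from the primary test even when a parent's Yes or an AE/SAE record points to fever

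*SAP*

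**What the plan says.** SAP 4.1.2 derives the primary endpoint by three rules and says it is "derived based on a conservative approach":

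- One daily measurement at or above 100.4°F gives fever=Yes.
- One or more readings, all below 100.4°F, together with a parental No, give fever=No.
- "If all days during the solicited period have missing body temperatures, then the value of fever=Missing". The sentence goes on: "even if the parent/guardian of the subject answered 'No' to the presence of fever".

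SAP 4.4.1.1.3 keeps a child with at least one non-missing presence and leaves out a child for whom presence is missing throughout. For solicited reactions, SAP 5.1.3.1 states that "the denominator will be the total number of subjects who have non-missing data for the endpoint considered". SAP 5.3.1 and 5.3.1.3 rule out imputation. The only extra analysis of the primary endpoint, in SAP 5.1.1.2, leaves out Site 009; none addresses missing temperatures.

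Fever evidence can also sit elsewhere in the data. Protocol 9.3.1.1 makes febrile convulsions SAEs. Protocol 9.3.1.3.2 codes provider contact and hospitalization as actions taken for solicited reactions.

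**The concern.** The clause about a parental No prevents an unmeasured No from being counted as no fever. That guards against dilution of the rate and is conservative. The condition of the rule, however, is only that all temperatures are missing, so a parental Yes, or a fever documented in an AE or SAE record, meets it equally. Removing such a child takes out a probable event.

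The primary test passes when the upper confidence bound for the excess of fever in the 0.5-mL arm is below 5%, so lost fevers in that arm favour a pass. This works against the stated conservative aim and against SAP 5.1.3.1, which chooses its denominators to avoid understating incidence. SAP 5.3.1 also says all safety data in the eCRFs enter the safety analyses, and the SAP does not reconcile that with this derivation.

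**Working it through.** **1. The rules set against the possible cases**

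| Daily temperatures in the window | Parent's answer or other record | Result under SAP 4.1.2 |
|---|---|---|
| Any ≥ 100.4°F | any | Yes |
| At least one, all < 100.4°F | No | No |
| At least one, all < 100.4°F | Yes | fits none of the three rules |
| None | No | Missing (stated) |
| None | Yes | Missing (by literal reading) |
| None | AE/SAE record with ≥ 100.4°F | Missing (by literal reading) |

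For a two-dose child, SAP 4.4.1.1.3 implies that both windows must be empty before the child is excluded. If one window has readings without fever and the documented fever is in the other, the child stays in the denominator but the event is not counted.

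**2. Inputs for the size of the effect**

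- From the documents: about 1095 per arm (SAP 3.2); 5% margin and Wilson score interval without continuity correction (SAP 5.1.1.2).
- Not available: the sample-size sections (Protocol 12.5, SAP 5.5) are redacted, so there is no planned fever rate or missing-data rate to reproduce. The rates below are assumptions.

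With p₂ the 0.5-mL rate, p₁ the 0.25-mL rate, d = p₂ − p₁, u₂ the upper Wilson limit for p₂ and l₁ the lower Wilson limit for p₁:

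upper bound = d + √[(u₂ − p₂)² + (p₁ − l₁)²]

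**3. Where the margin lies** (about 12% fever in the 0.25-mL arm, 1095 per arm)

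- 154 vs 131 fevers: 4.93%, pass.
- 155 vs 131: 5.02%, fail.
- 131 vs 131: 2.73%, pass.

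**4. Restoring lost fevers** (3% per arm without readings: 1095 × 0.97 ≈ 1062)

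For 149 vs 127 of 1062: p₂ = 14.03%, u₂ = 16.25%, p₁ = 11.96%, l₁ = 10.14%, d = 2.07. The bound is 2.07 + √(2.22² + 1.82²) = 4.94%.

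| Observed (of 1062 each) | Bound before | Fevers restored (0.5 vs 0.25 mL) | Bound after |
|---|---|---|---|
| 149 vs 127 | 4.94% | 5 vs 2 | 5.20%, fail |
| 149 vs 127 | 4.94% | 2 vs 1 | 5.03%, fail |
| 149 vs 127 | 4.94% | 5 vs 5 | 4.96%, pass |
| 138 vs 127 | 3.9% | 5 vs 2 | 4.12%, pass |
| 127 vs 127 | 2.77% | 5 vs 2 | 3.04%, pass |

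**5. How many lost fevers would tip the result** (10% control rate; all missing children restored to 1095 per arm; fevers only among the missing 0.5-mL children)

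| Observed difference | 2% missing (22 per arm) | 5% missing (55 per arm) |
|---|---|---|
| 0 points | cannot tip | 27 |
| +1 point | 15 | 17 |
| +2 points | 4 | 6 |

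**6. Type I error at the margin** (true rates 10% vs 15%, normal approximation)

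If a share f of fevers is lost, the observed rate becomes q = p(1 − f)/(1 − pf). The one-sided error is Φ[(0.05 − (q₂ − q₁))/SE − 1.96].

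| f | Same share lost in both arms | Lost in the 0.5-mL arm only |
|---|---|---|
| 0 | 0.025 | 0.025 |
| 2% | 0.028 | 0.038 |
| 5% | 0.034 | 0.067 |
| 10% | 0.047 | 0.153 |

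**The case against.** The strongest reply is that the rule is hard to trigger and that the evidence is not lost to the trial.

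- All eight days must be blank, and for a two-dose child both windows. Parents receive a thermometer, are told to measure daily and at any apparent fever, and are telephoned around Day 8.
- The rule tests temperatures in the eCRF, not a blank diary. Protocol 11.1 lets information absent from the diary reach the eCRF through the source document, and Protocol 13.2 has missing diary data clarified verbally and transferred. This stands, and it should keep the number small. Neither section says that a temperature from an AE or SAE report must be entered in the daily field, so the gap narrows but does not close.
- A reader might infer that severe fevers disappear from the trial. They do not: febrile convulsions and other SAEs are tabulated by group (SAP 5.1.3.1). They can be absent only from the primary fever rate.
- A reader might infer that the SAP expressly sets aside a parental Yes. It names only No; the Yes and AE/SAE cases follow from the literal rule. Nor do the documents show that hospitalized children are less likely to have home readings.
- The changes of outcome in the arithmetic need a near-margin result and more lost fevers in the 0.5-mL arm, both assumed. This stands.

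**Conclusion.** The point holds in a limited form. On its wording, SAP 4.1.2 misclassifies some children with evidence of fever as Missing. A child with no reading in any window then leaves the primary test. For these children the derivation is not conservative, and no planned analysis would show the effect.

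The number of such children is not in the documents and is probably small. With no observed difference the result is robust: at a 10% control rate and 2% missing per arm, it cannot tip. With an observed difference near 2 points, 4 to 6 uncounted fevers confined to the 0.5-mL arm would suffice at 2% to 5% missing. All of this rests on assumed fever and missing-data rates.

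The documents do not support going further and making an unmeasured parental Yes an event in the primary analysis. The endpoint is defined by a temperature threshold, so that choice is debatable and belongs in a sensitivity analysis.

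**What to change.** Amend SAP 4.1.2 in two places.

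1. Set fever=Yes also when any eCRF or eSAE record documents a temperature of at least 100.4°F on Day 0–7 after either dose, whether or not the daily field is filled.
2. Pre-specify a sensitivity analysis of the primary test that counts as fever=Yes any child with a parental Yes and no qualifying temperature. This should cover both cases: all readings missing, and all readings below 100.4°F, which the three current rules leave unclassified.

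The cost is a merge of data already collected and one extra analysis. Reported fever rates may rise slightly.

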## 4.2 Secondary Endpoints and Assessment Methods

The secondary immunogenicity objective is presented in [Section 2.2](#).

### 4.2.1 Immunogenicity Endpoints

- Geometric mean titers (GMTs): The hemagglutination inhibition (HAI) GMTs (for each of the 4 virus strains) at 28 days after the final vaccination.
- Seroconversion rates: The percentages of subjects with either a pre-vaccination titer < 10 (1/dil) and a post-vaccination titer  $\geq$  40 (1/dil), or a pre-vaccination titer  $\geq$  10 (1/dil) and a  $\geq$  4-fold increase in post-vaccination titer at 28 days after the final vaccination.

### 4.2.2 Immunogenicity Assessment Methods

#### *Antibodies to Influenza Viruses*

Anti-influenza antibodies will be measured by HAI performed by Sanofi Pasteur's Global Clinical Immunology (GCI) department or an external testing laboratory under GCI's supervision. Serum samples and quality control sera (sheep and/or human sera) will be incubated with Sigma Type III NA (receptor-destroying enzyme, neuraminidase type III from *Vibrio cholerae*) to eliminate non-specific inhibitors. Adsorption of spontaneous anti-species agglutinins will be performed by incubating the serum samples and quality control sera with a red blood cell (RBC) suspension. Following this, the mixtures will be centrifuged and the supernatants containing the treated sera will be collected for testing. Ten 2-fold dilutions (starting at 1/10) of the treated serum samples and quality control sera will be incubated with a previously titrated influenza virus solution at a concentration of 4 hemagglutination unit (HAU)/25  $\mu$ L. Influenza virus solution will not be added to the serum control wells containing only serum and RBCs. The mixture will be incubated and a RBC suspension will be added. Following incubation, the results will be read. The endpoint of the assay is the highest serum dilution in which complete inhibition of hemagglutination occurred. Each serum sample will be titrated in independent duplicates, and the 2 values, which do not differ by more than one 2-fold dilution, will be reported. The GMT between the 2 values will be calculated after the release of the data to the Clinical Data Management (CDM) platform. The lower limit of quantification (LLOQ) for HAI is set at 10, the lowest serum dilution used in the assay i.e., 1/10. Titers below this level are reported as < 10.

